## 2. Introduction

### 2.1. Background

ALS is an adult-onset degenerative motor neuron disorder leading to progressive motor deficits and eventually to death within a few years (Brown et al. 2017). Currently, there is no effective disease modifying drug available. A distinction is made between sporadic and familial ALS (Kiernan et al. 2021). Sporadic ALS (sALS) refers to the occurrence of ALS in a single individual without known family history of ALS or frontotemporal dementia (FTD). Reportedly, population genetic studies in ALS found sALS in more than 90% of all ALS patients (Brenner et al. 2019, Kim et al. 2020, Volk et al. 2017, Zou et al. 2017). The term "familial ALS" (fALS) relates to the occurrence of ALS or FTD in several family members of a given trait. The definition of fALS encompasses positive cases of FTD as this neurodegenerative disorder may share common pathogenic pathways with ALS.

In patients with sALS, genetic tests for SOD1, C9orf72, TARDBP or other genes are not subject to standard care. The previous findings on the frequency of genetic variants in ALS-associated genes can be traced back to a few populations genetic studies of ALS (Volk et al., 2018). As a result, sALS patients and treating neurologists are commonly unaware of the patient's mutation status. Even in patients with positive or uncertain family history of ALS or FTD, screening for genetic mutations is not performed on a regular basis. Reportedly, ALS-associated genetic variants are mostly found in the genes of SOD1, C9orf72, FUS, and TARDP (Brenner et al. 2019, Kim et al. 2020, Volk et al. 2017, Zou et al. 2017). More specifically, mutations in SOD1 were found in 14.8% of patients with fALS and 1.2% of the sALS population. The disease is causing repeat expansions of the C9orf72 gene, among which 6.5% are identified of the total ALS cohort (34% of fALS, 5% of sALS) (Zou et al. 2017).

Most of the data on the prevalence of genetic variants in ALS genes are derived from European studies and deduced to the German ALS population. Furthermore, previous studies where confined – or focused – on families with fALS, whereas the frequency of gene mutations in sALS has not been systematically investigated. In the result, the actual frequency of gene mutations in ALS, particularly in sALS, is basically unknown. It is well conceivable that the frequency of SOD1, C9orf72, FUS, and TARDP might be underestimated. Moreover, fALS may be more frequent than expected as family history is not always obtained by scrutiny leading to an uncertain number of fALS patients being undetected. Given the few systematic data on genetic variants in fALS and sALS, little is known about the clinical, prognostic and interventional characteristics genetically defined cohorts in ALS.

### 2.2. Study rationale

There is only limited data available on the frequency of genetic variants in patients with ALS. In patients with sALS, genetic testing is not subject of standard of care. As a result, the patient's mutation status is commonly unknown. Even in patients with fALS, screening for genetic mutations is not performed on a regular basis, as there are no genetically defined treatment options available. However, this paradigm is about to be changing as controlled clinical trials on genetic medicines are ongoing which might be approved in the future (Kiernan et al. 2021, Miller al et. 2021, Hardiman et al. 2020). This project is intended to investigate a large cohort of ALS patients on family history, clinical characteristics, health care measures and genetic variants in SOD1, C9orf72, FUS and TARDBP. This cohort study will allow to determine the frequency of gene mutations in ALS patients in a real-world setting of ALS centers in Germany. Furthermore, the project shall enhance insights into potential differences between genetically defined cohorts by means of the course of disease and the provision of health care measures. The investigation of genetically distinct ALS cohorts is particularly relevant, as an improved under-

standing of the relationship between the genotype and the journey of disease is scientifically indispensable, in order to determine the therapeutic potential of future genetic therapies.

### **2.3. Own previous work**

#### **2.3.1 ALS center at the Charité – Universitätsmedizin Berlin (principal investigator)**

The ALS center at the Charité was founded in 2002 by the principal investigator (PI) and evolved to a multidisciplinary care center serving more than 700 ALS patients. A major emphasis of the PI and his team has been the contribution to industry-sponsored and investigator-initiated trials. Prototyping, service engineering and implementation of digital and web-based solutions for managed care in ALS and other complex neurological disorders, such as Spinal Muscular Atrophy (SMA) has been realized since 2010. A current emphasis is on outcome research by means of biomarkers (large-scale investigation on neurofilament light-chain), patient reported outcomes (on innovative drugs, assistive technology devices), digital outcome markers (including sensory recognition of voice and facial expression in ALS) and clinical research with a main focus on medicines, ventilation intervention, robotic assistive systems in ALS (Meyer et al. 2018, 2019, 2020, Spittel et al. 2020).

#### **2.3.2 APST (Sponsor)**

APST was founded in 2010, being a spin-off of the ALS Center at the Charité. The digital platform “Ambulanzpartner” is the main product of APST. It serves as a digital case management and research platform with a main focus on ALS, SMA and other related disorders (Fürstenau et al, in press). The APST platform is used in more than 20 specialized care centers in Germany, serving as a digital demand platform and case management architecture connecting patients, neurological centers and health care providers. Since March 2011, more than 6.000 ALS patients and +200 subjects with adult 5q-SMA have been registered. More than 300.000 provisions of assistive devices, medicines and nutrition products have been managed at this platform. Beyond case management, the platform is being used for clinical research (Meyer et al. 2018, 2019, 2020; Holm et al. 2013), systematic analysis of health care provision (Funke et al. 2015; Funke et al. 2018) and digital assessment of patient reported outcomes, such as online capture of ALS functional rating scale (Maier et al. 2012). At the platform, the infrastructure for online assessment, in terms of legal framework, technology, usability and long-term experience, has been established. With the use of APST, a bi-directional digital communication with patients and the online assessment of questionnaires, scores and scales are facilitated. Thus, the ALS-FRS will be obtained during this study, by means of the “ALS App” smart phone application, which has been implemented recently.

## **3. Objectives and endpoints**

### **3.1. Objectives**

#### **3.2. Primary objective**

- To identify the frequency of genetic variants in the genes of SOD1, C9orf72, FUS and TARDBP in patients with sALS and fALS

#### **3.3. Additional objectives**

The additional objectives of this study are as follows:

- To investigate the demographic and social characteristics
- To investigate the family history for ALS or FTD
- To investigate the clinical classification, functional deficits, disease progression and health care measures in a subset of ALS patients with pathogenic variants in the genes of SOD1

or C9orf72 as compared to ALS patients with no ALS-associated mutations in the investigated genes

- To register available data on serum concentration of neurofilament light chain (sNfL)
- To register the history of interventions and health care measures including percutaneous endoscopic gastrostomy (PEG) and ventilation therapy
- To register the provision with assistive technology devices, symptomatic pharmacotherapy and physical, occupational and speech therapy
- To identify patient's treatment expectations towards ALS therapy using the Measure Your Medical Outcome Profile (MYMOP2)

### **3.4. Endpoints**

#### **3.4.1. Primary endpoints**

- Genetic variants in the genes of SOD1, C9orf72, FUS and TARDBP

#### **3.4.2. Additional endpoints**

- The following additional endpoints will be explored:

##### *Demographic data, disease history and social setting*

- Age, gender, place of residence
- Disease onset and duration
- Education, employment, housing

##### *Family history of ALS and FTD*

- Family members living with ALS or FTD
- Family members who have died from ALS or FTD

##### *Clinical classification*

- ALS subtypes (classic ALS, progressive muscular atrophy (PMA) and primary lateral sclerosis (PLS))
- Type of onset (bulbar region, trunk or extremities)

##### *Functional deficit and progression*

- ALS Functional Rating Scale (ALS-FRS)
- ALS progression rate (loss of ALS-FRS per months)
- King's classification of clinical stages of ALS
- Serum concentration of neurofilament light chain (sNfL)

##### *Interventions and health care measures*

- Percutaneous endoscopic gastrostomy (PEG)
- Non-invasive ventilation
- Tracheostomy
- Provision with assistive technology devices
- Symptomatic pharmacotherapy
- Physical, occupational and speech therapy

##### *Patient's expectations towards ALS therapy*

- Measure Your Medical Outcome Profile (MYMOP2)

This evaluation is exploratory. There is no formal hypothesis that is tested.

## **4. Overall study design**

### **4.1. Study design**

This is a longitudinal, non-interventional, non-randomized, multicenter, prospective study conducted in subjects with ALS. Duration of study participation for each subject will be up to approximately 12 months. Subjects will be enrolled to receive questionnaires, in order to assess the variables and to provide blood samples for molecular genetic testing. Approximately 1,000 subjects are planned to complete the study. It is anticipated that up to approximately 18 sites will be activated in Germany. This registry study will be reported according to STRO-BE-statement.

### **4.2. Participating centers**

The study follows a multicenter research trial. Results will be conducted at approximately 18 ALS centers in Germany participating in the observation study. ALS centers in different geographical regions of Germany will be activated:

- Northern Germany: Berlin, Hannover, Rostock, Lübeck
- Eastern Germany: Dresden, Jena, Halle, Leipzig
- Western Germany: Essen, Bonn, Göttingen, Münster, Bochum,
- Southern Germany: Ulm, München, Mannheim

### **4.3. Overall study duration and assessments**

The study will include ALS patients at specialized outpatient clinics (study sites). All subjects will undergo 3 assessments over a period of approximately 12 months. The assessment schedule will be as follows:

- Assessment at baseline: initial assessment of subjects including blood sampling and molecular genetic analysis
- Assessment at follow-up: follow-up assessment that is realized in a 6-month interval
- Assessment at the end of the study: final assessment after 10 to 14 months interval and optional

  

- Assessment for interim analysis: interim analyses performed for this study at variable time points, at least after all subjects complete the 6-month assessments.

### **4.4. Study stopping rules**

Not applicable for an observational study.

## **5. Study subjects**

### **5.1. Number of study subjects**

2,000 subjects are planned to be recruited. More than 1000 subjects are expected to complete the end-of-study assessments, after an observation period of 12 months.

### **5.2. Inclusion criteria**

Being eligible to participate in this study, study candidates must meet the following eligibility criteria at the baseline assessment:

- ALS, including classical ALS, Progressive Muscle atrophy (PMA) or Primary Lateral Sclerosis (PLS)
- Ability to understand the purpose and risks of the study and provide signed and dated informed consent and authorization to use protected health information (PHI) in accordance with national and local subject privacy regulations
- Age of 18 years old at the time of informed consent

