### **6. Enrollment of subjects**

The enrollment of subjects takes place in specialized ALS-outpatient centers in Germany. ALS patients being eligible for the investigation, will be invited to participate in this cohort study. After obtaining informed consent, subjects will be enrolled in the study. Approximately, 2,000 subjects will be observed in this study. Participating sites will be informed once 2,000 subjects have been enrolled.

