## **11. Statistical methods and analysis plan**

Descriptive statistics will be presented for each assessment of all subjects at study visit. Subgroup analyses by genetic or clinical criteria or other baseline characteristics will be performed. Secondary endpoints in the genetically defined subsets of ALS with confirmed SOD1 or C9orf72 mutations will be compared to genetically tested patients with ALS not revealing any ALS-associated mutation in any of the tested genes. Descriptive statistics will be used for the statistical analysis (frequency in percentage, mean, median, standard deviation in  $\pm$ , interquartile ranges (Q1, Q3), and ranges (min, max). The standardized mean difference (SMD) will be applied in this study. The SMD of each measure over up to 12 months will be estimated using the change in measure between each subject's assessments and within each individual. The standardized mean difference expresses the size of intervention effect. Difference of frequencies between two groups will be assessed by Fisher's exact test or Chi-square test, or within metric data by using the Shapiro-Wilk test, Kruskal-Wallis test and Mann-Whitney U-test. The Wilcoxon test will be employed for the analysis of statistical power of ordinal-scaled data, while metric data were subjected to the t-test (ALS-FRS, MYMOP). This analysis applies to the comparison of genetically defined subsets of ALS (baseline characteristics and changes over time). The analysis of follow-up data is limited to complete

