cases, since not all patients are expected to complete end-of-study assessments due to disease progression, e.g., death. It is aimed to compare the baseline characteristics and the proportion of death between those who completed and not those not completed 6 months and 12-month assessment. Statistical significance will be ascertained by according to an error risk of up to 5% (p-value < 0.05). Associations for the clinical outcomes will be assessed by linear regression models adjusted for potential confounding factors. Results of the longitudinal observations will be also controlled for the influence of any covariate (sex, age, intervention history). Longitudinal analysis by means of group comparisons will be applied by using a multivariate analysis. 95% confidence intervals with p-values will be reported. In order to draw conclusions from the samples with censored data, missing data records will be omitted and treated as missing values. Data analysis will be performed using SPSS (Version 25.0).

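### The primary mutation frequency mixes patients of any disease duration, so it may differ from the frequency among newly diagnosed patients, and the plan includes no table that would show this

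*Combined protocol and SAP*

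**What the plan says.** **Who is enrolled.** Section 5.2 asks for "ALS, including classical ALS, Progressive Muscle atrophy (PMA) or Primary Lateral Sclerosis (PLS", plus age and consent. The exclusions in section 5.3 do not mention disease duration. Section 6 adds only that "ALS patients being eligible for the investigation, will be invited to participate in this cohort study". There is no incident-case rule and no consecutive-enrolment rule.

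**What is estimated.** The primary objective (section 3.2) is "To identify the frequency of genetic variants in the genes of SOD1, C9orf72, FUS and TARDBP in patients with sALS and fALS". Section 11 gives the summary: "Descriptive statistics will be used for the statistical analysis (frequency in percentage, mean, median" and so on. Adjustment is reserved for other results: "Associations for the clinical outcomes will be assessed by linear regression models adjusted for potential confounding factors". Section 11 also has a general clause, "Subgroup analyses by genetic or clinical criteria or other baseline characteristics will be performed", which names neither disease duration nor the mutation frequency.

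**What the figure is meant to represent.** Section 2.2 says "This cohort study will allow to determine the frequency of gene mutations in ALS patients in a real-world setting of ALS centers in Germany". Section 2.1 motivates the study more broadly, on the ground that "the actual frequency of gene mutations in ALS, particularly in sALS, is basically unknown".

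**What is collected.** Table 1 and Table 4 include date of onset, date of diagnosis and disease duration at baseline, recorded to the month.

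**The concern.** When patients can enrol at any point in their illness, those who live longer are available for enrolment longer. If carriers of a variant live longer or shorter than other patients, their share of such a sample differs from their share among newly diagnosed patients.

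The protocol supplies both links in this chain, qualitatively. Section 12.3.1, in defining diagnostic relevance, includes variants that may alter the rate of progression. Section 9.6.2 states that the progression rate predicts survival. Differences between genotypes in disease course are themselves a topic of the study (sections 2.2 and 3.3).

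What is at stake is how the main result is read. Section 2.1 sets the study against published frequencies and suggests that they may be too low. If the registry figure differs from them, a reader could not tell whether the cause is genetics or the mix of disease durations. More patients would narrow the interval but would not resolve this.

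**Working it through.** **The plan's own figure.** The documents give no precision, power or bias figure for the primary frequency. The 2,000 subjects are stated to rest on feasibility, so there is nothing to reproduce. The check below asks how large the effect could be.

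**Inputs from the documents**
- C9orf72: 6.5% overall, 34% in fALS, 5% in sALS (section 2.1).
- SOD1: 14.8% in fALS, 1.2% in sALS (section 2.1).
- n = 2,000 (section 5.1).
- Study period: described as about two years, with dates August 2021 to December 2024, which span 41 months (synopsis).

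**Overall SOD1 frequency.** The C9orf72 figures imply an fALS share f: 0.05 + (0.34 − 0.05)f = 0.065, so f = 0.015/0.29 = 5.2%. This agrees with the statement in section 2.1 that more than 90% of cases are sporadic. With that share, SOD1 overall = 0.012 + (0.148 − 0.012) × 0.052 = 1.9%.

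**Assumptions not in the documents**
- Ratio r of mean disease duration, carriers to non-carriers: 0.75 to 1.5.
- Mean duration D0 in non-carriers: 24 to 48 months.
- Recruitment window T: 24 to 41 months, in line with the two descriptions of the study period.
- Every patient under care at some time in the window is equally likely to enrol.

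**Formulas.** The eligible pool holds patients already ill at the start and new cases during the window, so the effective ratio is

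r_eff = (r × D0 + T) / (D0 + T).

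The observed frequency, for true frequency p at diagnosis, is

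p* = p × r_eff / (p × r_eff + 1 − p).

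**Worked case.** With r = 1.5, D0 = 48, T = 24: r_eff = (72 + 24)/72 = 1.333. For C9orf72, p* = 0.08667/(0.08667 + 0.935) = 8.48%.

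**Results over all D0 and T**

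| r | C9orf72, true 6.5% | shift (points) | SOD1, true 1.9% | shift (points) |
|---|---|---|---|---|
| 0.75 | 5.48% to 5.94% | −1.02 to −0.56 | 1.59% to 1.73% | −0.31 to −0.17 |
| 1 | 6.50% | 0 | 1.90% | 0 |
| 1.5 | 7.61% to 8.48% | +1.11 to +1.98 | 2.25% to 2.52% | +0.34 to +0.62 |

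A simulation with D0 = 36, T = 29 and exponential durations agreed: at r = 0.75 it gave 5.69%, against 5.65% from the formula.

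**Sampling error for comparison.** The 95% half-width is 1.96 × √(p(1 − p)/2000):
- C9orf72: 1.96 × √(0.065 × 0.935/2000) = 1.08 points.
- SOD1: 1.96 × √(0.019 × 0.981/2000) = 0.60 points.

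At r = 0.75 the shift stays inside the half-width for both genes. At r = 1.5 it exceeds the half-width for C9orf72 throughout. For SOD1 it reaches the half-width only at the far end of the range.

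**The case against.** **The target may be clinic patients.** Section 2.2 speaks of patients in the real-world setting of German ALS centers. For that population the mix of durations is part of the quantity, not an error. This stands, and it rules out calling the primary result wrong. The documents do not say whether newly diagnosed or current patients are meant, and section 2.1 speaks of ALS as a whole, so the figure needs a label.

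**Direction and size are unknown.** A reader might infer that slow genotypes are over-counted and fast ones under-counted as a matter of fact. The documents give no survival or duration by genotype. They say only that variants may alter progression, and that differences between genotypes are potential. At r = 1 nothing happens.

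**Larger figures overstate the effect.** A purely prevalent sample with r from 0.5 to 2 would turn 6.5% into 3.4% to 12.2%, and 1.9% into 1.0% to 3.7%. That is an upper bound for that range of r, because recruitment over a window of years also takes in new cases. Enrolment at outpatient centers of patients able to comply also means that time alive is not exactly the sampling weight.

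**The plan is not confined to one pooled figure.** The objective names sALS and fALS, and the subgroup clause in section 11 is broad enough to cover disease duration. This stands in part: such a table is allowed, but it is neither named nor tied to the primary frequency.

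**Comparability with the literature.** One might infer that the result cannot be compared with published frequencies. The documents do not say how the cited studies sampled their patients, so that conclusion is not supported.

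**Conclusion.** The point holds as a risk to interpretation, not as a demonstrated bias. Entry is open to any disease duration, the frequency is planned as an unadjusted percentage (inferred, since no dedicated primary analysis is written), and the protocol itself makes a link between genotype and survival plausible.

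For duration ratios between 0.75 and 1.5, C9orf72 could be read about 1 point low or 2 points high, against a half-width of 1.1. SOD1 could be read about 0.3 points low or 0.6 high, against 0.6. These figures rest on the assumed ratios, durations and recruitment window, and for SOD1 on an fALS share of about 5%. The true ratio for each gene is not in the documents.

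A reader might also infer that survival or time-to-intervention comparisons need correction for delayed entry. Section 11 plans no such analysis, so that advice does not apply.

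**What to change.** In section 11:

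1. Label the overall mutation frequency as the frequency in patients under care at the participating ALS centers.
2. Pre-specify one added table: frequency per gene with 95% confidence intervals, separately for sALS and fALS, in patients enrolled within a pre-set time of diagnosis (for example 12 months) and by category of time from diagnosis to V1. Fix the categories before the data are analysed.

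If the frequency is similar across the categories, the mix of durations is unlikely to matter. If it is not, the newly diagnosed figure is the one to set beside frequencies in newly diagnosed patients elsewhere.

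**Cost.** No new data, visits or change to eligibility are needed, because Table 4 already records the dates. The price is precision. If, for illustration, a quarter of the cohort (500) were newly diagnosed, half-widths would double (√(2000/500) = 2), to about 2.2 points for C9orf72 and 1.2 for SOD1. The fALS cells will be sparse. At a 5.2% share there are about 103 fALS patients in the whole cohort, and the C9orf72 half-width at 34% is already 1.96 × √(0.34 × 0.66/103) = 9.1 points before any split by duration.
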